If the patient receiving talimogene laherparepvec (T-VEC) on study has developed signs or symptoms of herpetic infection, the event must be reported to Amgen AND CTEP-AERS and patient should be followed up by the study team for viral assays: Report to CTEP-AERS as SAE. **NOTE: Refer to Section 18.3 for Additional Reporting Requirements**

- h. Reporting Secondary Malignancy, including AML/ALL/MDS
 - 1. A secondary malignancy is a cancer caused by treatment for a previous malignancy (e.g., treatment with investigational agent/intervention, radiation or chemotherapy). A secondary malignancy is not considered a metastasis of the initial neoplasm.

CTEP requires all secondary malignancies that occur following treatment with an agent under an NCI IND to be reported via CTEP-AERS. Three options are available to describe the event.

- Leukemia secondary to oncology chemotherapy (e.g., Acute Myelocytic Leukemia [AML])
- Myelodysplastic syndrome (MDS)
- Treatment-related secondary malignancy

Any malignancy possibly related to cancer treatment (including AML/MDS) should also be reported via the routine reporting mechanisms outlined in each protocol.

Second Malignancy: A second malignancy is one unrelated to the treatment of a prior malignancy (and is NOT a metastasis from the initial malignancy). Second malignancies require ONLY routine reporting via CDUS unless otherwise specified.

For more information see: http://ctep.cancer.gov/protocolDevelopment/electronic_applications/d ocs/aeguidelines.pdf

2. Any supporting documentation should be submitted to CTEP per NCI guidelines for AE reporting located at http://ctep.cancer.gov/protocoldevelopment/electronic_applications/docs/aeguidelines.pdf

A copy of the report and the following supporting documentation must also be submitted to SWOG Operations Office within 30 days by fax to [contact] or mail to the address below:

- a copy of the pathology report confirming the AML/ALL /MDS diagnosis
- (if available) a copy of the cytogenetics report

SWOG ATTN: SAE Program [name]

NOTE: If a patient has been enrolled in more than one NCI-sponsored study, the report must be submitted for the most recent trial.

- i. Reporting Pregnancy, Fetal Death, and Death Neonatal
 - 1. **Pregnancy** Study participants who become pregnant while on study; that pregnancy should be reported in an expedited manner via CTEP-AERS as **Grade 3 "Pregnancy, puerperium and perinatal conditions Other** (pregnancy)" under the **Pregnancy, puerperium and perinatal** conditions SOC.

Additionally, the pregnancy outcome for patients on study should be reported via CTEP-AERS at the time the outcome becomes known, accompanied by the same Pregnancy Report Form used for the initial report.

- 2. Fetal Death Fetal Death defined in CTCAE as "A disorder characterized by death in utero; failure of the product of conception to show evidence of respiration, heartbeat, or definite movement of a voluntary muscle after expulsion from the uterus, without possibility of resuscitation" should be reported expeditiously as Grade 4 "pregnancy, puerperium and perinatal conditions – Other (pregnancy loss)" under the Pregnancy, puerperium and perinatal conditions SOC.
- 3. **Death Neonatal** Neonatal death, defined in CTCAE as "A disorder characterized by cessation of life occurring during the first 28 days of life" that is felt by the investigator to be at least possibly due to the investigational agent/intervention should be reported expeditiously.

A neonatal death should be reported expeditiously as **Grade 4** "**General disorders and administration – Other (neonatal loss)**" under the **General disorders and administration** SOC.

Fetal death and neonatal death should **NOT** be reported as a Grade 5 event. If reported as such, the CTEP-AERS interprets this as a death of the patient being treated.

NOTE: When submitting CTEP-AERS reports for "Pregnancy, "Pregnancy loss", or "Neonatal loss", the Pregnancy Information Form should also be completed and faxed with any additional medical information to [contact]. The potential risk of exposure of the fetus to the investigational agent(s) or chemotherapy agent(s) should be documented in the "Description of Event" section of the CTEP-AERS report.

The Pregnancy Information Form is available at: http://ctep.cancer.gov/protocolDevelopment/adverse_effects.htm

j. Additional Reporting Requirements for T-VEC-associated adverse events and biosafety incidents.

Please see Appendix 18.3.

17.0 **BIBLIOGRAPHY**

18.1 Anti-PD-1 and Anti-PD-L1 Agents

- Atezolizumab
- Avelulmab
- Durvalumab
- Nivolumab
- Pembrolizumab (MK-3475)

- 18.2 Translational Medicine Methods
 - 1. **Data storage and computational infrastructure:** To optimally perform computational analysis on the large amount of genomic and imaging data to be generated from this study, it is expected that appropriate cloud computing infrastructure with the necessary analysis pipeline is required for the storage and computation of these data. One such computational infrastructure and resource available for this study is through the collaboration with the Parker Institute for Cancer Immunotherapy.
 - 2. Quantitative analysis of T-cell infiltration: Given local virus replication and GM-CSF release, we anticipate increased CD8+ Tcell infiltration in the tumors after combination of intratumoral injection of talimogene laherparepvec (T-VEC) and PD-1 blockade starts. Slides taken from standard formalin-fixed paraffinembedded (FFPE) tissue blocks obtained from baseline, Day 28 (on treatment), and upon progression to determine the presence of CD8+ T-cells inside tumors and in the invasive margin. Slides will be analyzed using quantitative digital pathology following the methods described. *(1)*

All slides will be scanned at an absolute magnification of X200 (resolution of 0.5 mm/pixel). An algorithm was designed based pattern on recognition that quantified immune cells within S100positive areas (tumor) and S100negative areas (invasive margin). Image analysis based on RGB (red, green, blue)

spectra will be used to detect all cells by counterstaining with haemotoxylin (blue), and DAB or fast red. CD8 expression is determined using two read-outs that are independent of each other to account for tumor heterogeneity: cell density (number of positive cells /mm²) and percentage cellularity (number of positive cells/number of nucleated cells) using Indica Labs Halo platform.

3. Analysis of TCR clonality in tumors and in blood: To answer the question whether the T-cell response is targeting specific tumor antigen (mono-clonal) or a non-specific process (poly-clonal) in both the tumors and in the peripheral blood, we will analyze TCR clonality by deep sequencing the TCR V β CDR region using the ImmunoSeq assay from Adaptive Biotech as described. (2) PBMC from blood and thick slides from FFPE tissues taken at baseline and Day 28 after initiation of treatments, will be used to isolate DNA for TCR V β sequencing. This analysis will provide information about the clonality or diversity of T-cells infiltrating tumors and circulating in the blood. DNA analysis will be performed by the UCLA Immunogenetics core laboratory (CLIA approved lab).

DNA will be isolated from FFPE thick cuts or PBMC followed by extraction using a DNeasy kit (Qiagen). Melanin will be removed from visibly pigmented melanoma samples using a PCR Inhibitor Removal kit (ZymoResearch). TCR V β CDR3 regions will be amplified and sequenced using the survey ImmunoSeq assay in a multiplexed PCR method using 45 forward primers specific to TCR V β gene segments and 13 reverse primers specific to TCR V β gene segments (Adaptive Biotechnologies). Reads of length 87bp will be obtained using the Illumina HiSeq System. For each sample, Shannon entropy will be calculated on the clonal abundance of all productive TCR sequences in the data set. Shannon entropy will be normalized to the range by dividing Shannon entropy by the logarithm of the number of unique productive TCR sequences in the data set. This normalized entropy value will be then inverted (normalized entropy) to produce our clonality metric.

4. Analysis of tumor immune microenvironment: Local viral replication and antigen presentation, as well as GM-CSF release, will attract dendritic cell infiltration, and change the global tumor immune microenvironment in favor of activating the immune system to target the tumor. In addition, interferon produced by inflammatory cells in an attempt to eradicate the viral infection, can up-regulate PD-L1 expression, providing rationale for synergy of talimogene laherparepvec (T-VEC) with PD-1 blockade.

Slides taken from standard FFPE tissue blocks obtained from baseline, the ontreatment biopsy (Day 28) and upon progression will be stained by IHC for PD-L1 (SP142, Spring Bioscience), PD-1, dendritic cell markers (CD80, CD86), immune suppressive cell markers (anti-FoxP3 for Treg, anti-CD68 antibody for macrophage, clone PG-M1, DAKO, anti-CD14 for monocyte, CD15 for granulocytes), or other immune related functional expression and biomarkers. Slides will be analyzed using quantitative multiplexed digital pathology. *(3, 4)*

Immunostaining of the rest of the targets will be performed at the UCLA Anatomic Pathology IHC Laboratory (CLIA approved lab) on Leica Bond III autostainers using Leica Bond ancillary reagents and REFINE polymer DAB detection system. All stained slides will be evaluated in a blinded fashion by one dermatopathologist and one investigator trained to identify the features of melanoma, and the presence of positive stained targets within the tumor parenchyma (tumor) and the connective tissue surrounding the tumor (invasive margin).

Analysis of mRNA expression by Nanostring allowed demonstrating that an interferon gamma signature is predictive of response with pembrolizumab (5), which is logical as it is an indirect measure of a pre-existing infiltrate by T cell with specificity to tumor antigens leading to the production of interferon gamma and the adaptive expression of PD-L1. Further analyses of mRNA expression demonstrated a dominant set of genes in patients whose tumors did not respond to anti-PD-1, which we termed innate PD-1 resistance signature (IPRES). (6) We will consider to extract total RNA from FFPE samples and do nanostring analysis for global evaluation of immune activation. With these studies we anticipate to obtain a comprehensive view of the effects of the combined therapy of T-VEC and pembrolizumab to reverse resistance to single agent anti-PD-1 therapy.

5. Analysis of mutational load by whole exome sequencing:

It is currently unknown which antigens are being recognized by T-cells attacking tumors after release of PD-1 blockade. But evidence from studies with other immunotherapies suggests that most of these antigens are neoepitopes resultant from somatic mutations. In a recent experience, whole exome sequencing was performed on tumors and matching blood of patients treated with CTLA4 blockade

with ipilimumab or tremelimumab. (7) Neoantigen peptides were tested for the ability to activate lymphocytes from ipilimumab-treated patients. Mutational load was associated with clinical benefit (p=0.01), but alone was not sufficient to predict benefit. Using genome-wide somatic neoepitope analysis and patient-specific HLA typing, the authors identified candidate tumor neoantigens for each patient. Recently, a correlation of tumor mutational load and response to PD-1 antibody therapy was also reported in NSCLC patients treated with pembrolizumab (MK-3475). (^a) We want to evaluate whether tumor mutational load and circulating tumor DNA (ctDNA) profile are associated with response to talimogene laherparepvec (T-VEC) + pembrolizumab (MK-3475) combination in this anti-PD1 refractory melanoma population. In addition, since the IFN pathway is critically important for the efficacy of the talimogene laherparepvec (T-VEC) oncolytic viral therapy, we want to evaluate mutations in the IFN signaling pathway and the correlation with tumor specific immune response of the talimogene laherparepvec (T-VEC) + pembrolizumab (MK-3475) combination therapy.

DNA will be isolated from thick slides of FFPE tissues and *PBMC via commercial kit (i.e. Qiagen AllPrep DNA/RNA FFPE kit, cat 80234). Whole exome sequencing (WES), including probe-based exon capture, library preparation, and high throughput 100bp paired-end sequencing on the Illumina HiSeg2500 platform will be performed at the UCLA Immunogenetics core laboratory. DNA from the same patient's PBMC (preferably) or other non-cancerous tissue will be isolated and sequenced for baseline comparison and differentiation of germline SNPs from true somatic mutations. Read mapping and data preprocessing will be performed according to the Broad Institute Best Practices Guidelines for the Genome Analysis Toolkit (version 3), and mutation detection will require a consensus call among several published programs (Varscan2, MuTect, GATK HaplotypeCaller). Mutational load will be quantified as the number of nonsynonymous somatic mutations per MB. Circulating tumor DNA profiling from patient-matched baseline and on-treatment plasma samples will be performed to determine the amount or fraction of ctDNA corresponding to the genetic profile of the patient tumor biopsies. Taken together, this will evaluate whether tumor mutational load and circulating tumor DNA (ctDNA) profile are associated with response to talimogene laherparepvec (T-VEC) + pembrolizumab (MK-3475) combination in this anti-PD1 refractory melanoma population.

Translational Medicine Objectives

a. For all analyses, if the distributions are far from normal or subject to influential points, then we will use robust, rank based or non-parametric approaches such as the Wilcoxon test. Similarly, we will conduct adjusted analyses to accommodate any potential confounders that may arise, e.g. technical batch.

To assess whether there is a change in T-cell infiltration from baseline to Day 28, we compare CD8 expression levels between baseline and week 2 using a paired t-test. We will control type I error at the two-sided alpha=0.05 level. For Cohort A, with 17 eligible patients, we anticipate 80% power to detect a change in mean CD8 expression from baseline to Day 28 of 0.72 standard deviations. Among patients that progress, we will repeat the analysis to compare CD8 expression at progression to baseline with the understanding that there is potentially informative missingness in that patients who do not progress may have higher infiltration.

We will further assess whether increased T-cell infiltration from baseline to Day 28 is associated with higher ORR. Specifically, we will compute the change in CD8 expression between Day 28 and baseline and compare the change in CD8 expression between objective responders and non-

objective responders using a two-sample t-test at the two-sided 0.05 level. For Cohort A, with 17 eligible patients and assuming 25% of patients have a response, we anticipate 80% power to detect a difference in mean change in CD8 expression of 1.68 standard deviations. Subsequently, to assess the hypothesis that TCR clonality is higher in patients who respond to the combination therapy, suggesting that the T-cells are targeting the tumor, we will compute the clonality metric as the normalized Shannon entropy for all patients at baseline and Day 28. We will then compute the change in clonality metric from baseline to Day 28. The change in clonality will be compared between responders and non-responders using a twosample t-test with significance determined at the two-sided alpha=0.05 level. For Cohort A, assuming that 25% of patients respond, then we anticipate 80% power to detect a difference in clonality change of 1.68 standard deviations. We will repeat the analyses examining TCR clonality in peripheral blood. Finally, we will assess whether ctDNA fraction at baseline and Day 28 is associated with ORR using a two-sample t-test at the two-sided 0.05 level. For Cohort A, with 17 eligible patients and assuming 25% of patients have a response, we anticipate 80% power to detect a difference in mean ctDNA fraction of 1.68 standard deviations.

To assess whether the tumor microenvironment is improved by injection with talimogene laherparepvec (T-VEC), we will examine the expression of approximately 10 candidate immune markers: PD-L1, PD-1, dendritic cell markers (CD80, CD86), immune suppressive cell markers (anti-FoxP3 for Treg, anti-CD68 antibody for macrophage, clone PG-M1, DAKO, anti-CD14 for monocyte, and CD15 for granulocytes). For each marker, we will test for a difference in expression between baseline and the Day 28using paired t-tests at the alpha = 0.005 level to accommodate multiple comparisons. We will subsequently test the association between change in expression level of each marker (from baseline to Day 28) with response using a two-sample t-test at the alpha = 0.005 level. For Cohort A, in comparing expression at baseline to Day 28, with 17 eligible patients, we anticipate 80% power to detect a change in mean expression of 1.0 standard deviations. In comparing change in expression between responders and non- responders, assuming 25% of patients respond durably, then we anticipate 80% power to detect a difference in mean change in expression of 2.3 standard deviations.

To assess the hypothesis that higher mutational load at baseline or at Day 28 is associated with durable response rate, we will assess the association between overall mutational load at each time point, separately, and durable response rate. Specifically, we will use logistic regression to regress response status on the mutation rates (at baseline or at Day 28) and use a 1-df test to obtain a p-value for the association between durable response and mutation rate. We will control the type I error at the two-sided alpha=0.10 level. If logistic regression behaves poorly, e.g. due to low response rates, we will consider using robust or flexible alternatives.

b. For all analyses, if the distributions are far from normal or subject to influential points, then we will use robust, rank based or non-parametric approaches such as the Wilcoxon test. Similarly, we will conduct adjusted analyses to accommodate any potential confounders that may arise, e.g. technical batch.

To assess whether there is a change in T-cell infiltration from baseline to Day 28, we compare CD8 expression levels between baseline and Day 28 using a paired t-test. We will control type I error at the two-sided alpha=0.05 level. For Cohort B, with 25 eligible patients, we anticipate 80% power to detect a change in mean CD8 expression from baseline to Day 28 of 0.58 standard deviations. Among patients that progress, we will repeat the analysis to compare CD8 expression at progression to baseline with the understanding that there is potentially informative missingness in that patients who do not progress may have higher infiltration.

We will further assess whether increased T-cell infiltration from baseline to Day 28 is associated with higher ORR. Specifically, we will compute the change in CD8 expression between Day 28 and baseline and compare the change in CD8 expression between responders and non-responders using a two-sample t-test at the two-sided 0.05 level. For Cohort B, with 25 eligible patients and assuming 30% of patients have a response, we anticipate 80% power to detect a difference in mean change in CD8 expression of 1.28 standard deviations.

We will first assess whether TCR clonality within the tumor increases following treatment with combination therapy. Specifically, we will test for difference in mean normalized Shannon entropy for all patients between baseline and Day 28. For Cohort B, with 25 eligible patients, we anticipate 80% power to detect a change in mean normalized Shannon entropy from baseline to Day 28 of 0.58 standard deviations. We will repeat the analysis to compare TCR clonality at progression to baseline among patients who progress. Subsequently, to assess the hypothesis that TCR clonality is higher in patients who respond to the combination therapy, suggesting that the T-cells are targeting the tumor, we will compute the clonality metric as the normalized Shannon entropy for all patients at baseline and Day 28. We will then compute the change in clonality metric from baseline to Day 28. The change in clonality will be compared between responders and non- responders using a two-sample t-test with significance determined at the two-sided alpha=0.05 level. For Cohort B, assuming that 30% of patients respond, then we anticipate 80% power to detect a difference in clonality change of 1.28 standard deviations. We will repeat the analyses examining TCR clonality in peripheral blood. Finally, we will assess whether ctDNA fraction at baseline and Day 28 is associated with ORR using a two-sample t-test at the two-sided 0.05 level. For Cohort B, with 25 eligible patients and assuming 30% of patients have a response, we anticipate 80% power to detect a difference in mean ctDNA fraction of 1.28 standard deviations.

To assess whether the tumor microenvironment is improved by injection with talimogene laherparepvec (T-VEC), we will examine the expression of approximately 10 candidate immune markers: PD-L1, PD-1, dendritic cell markers (CD80, CD86), immune suppressive cell markers (anti-FoxP3 for Treg, anti-CD68 antibody for macrophage, clone PG-M1, DAKO, anti-CD14 for monocyte, and CD15 for granulocytes). For each marker, we will test for a difference in expression between baseline and the Day 28 using paired t-tests at the alpha = 0.005 level to accommodate multiple comparisons. We will subsequently test the association between change in expression level of each marker (from baseline to Day 28) with response using a two-sample t-test at the alpha = 0.005 level. For Cohort B, in

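### Fixed alpha of 0.005 per immune marker is a valid but inefficient rule for up to 10 markers; Holm's procedure over a locked marker list would recover some power at the same implied 5% family-wise level

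*Combined protocol and SAP*

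**What the plan says.** Both cohort items in Section 18.2 say of the immune microenvironment that "we will examine the expression of approximately 10 candidate immune markers". Each then names eight: PD-L1, PD-1, CD80, CD86, FoxP3, CD68, CD14 and CD15. The clone and supplier given beside CD68 describe that antibody and are not further markers.

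Two families of tests follow in each cohort:

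- Change from baseline to Day 28, using "paired t-tests at the alpha = 0.005 level to accommodate multiple comparisons".
- Association of that change "with response using a two-sample t-test at the alpha = 0.005 level".

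The stated detectable differences at 80% power are:

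- Cohort A (17 patients): 1.0 SD paired; 2.3 SD for the association, with 25% responding.
- Cohort B (25 patients): 0.80 SD paired; 1.73 SD for the association, with 30% responding.

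Section 18.2 item 4, which describes the staining, adds after its list of targets "or other immune related functional expression and biomarkers", so the panel is not closed. No step-down procedure is described. The sidedness of the 0.005 tests and the family-wise target are not stated. The CD8 analysis in the same section says "We will control type I error at the two-sided alpha=0.05 level".

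**The concern.** A cut-off of 0.005 equals 0.05/10, applied to every marker whatever the other results show. That is single-step Bonferroni. Holm's step-down procedure uses the same p-values, holds the same family-wise error under any correlation between markers, and relaxes the threshold after each rejection. With 17 and 25 patients, and roughly four and seven or eight responders, power is scarce. A rule that gives some of it up for no better guarantee of the implied 5% level deserves a second look. At stake is the chance of detecting true marker changes under objective 1.3c. The primary and secondary endpoints and the two-stage decision rules are unaffected.

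**Working it through.** **Inputs.** Alpha 0.005, the sample sizes, response rates and detectable differences come from Section 18.2 items a and b. Assumptions: two-sided tests (as for CD8) and a 5% family-wise target, inferred from 0.05/10.

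**Reproducing the plan's figures.** Detectable difference = (t at 1 − alpha/2 + t at 0.80) × standard error, with fractional responder counts (25% of 17 = 4.25; 30% of 25 = 7.5):

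- A paired, 16 df: (3.252 + 0.865)/√17 = 0.998 (stated 1.0)
- B paired, 24 df: (3.091 + 0.857)/√25 = 0.789 (stated 0.80)
- A association, 15 df: (3.286 + 0.866) × √(1/4.25 + 1/12.75) = 2.326 (stated 2.3)
- B association, 23 df: (3.104 + 0.858) × √(1/7.5 + 1/17.5) = 1.729 (stated 1.73)

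The two-sided reading therefore reproduces the plan. Noncentral-t power at the stated differences is 78.9%, 80.5%, 77.4% and 79.2%. With whole responders the associations have about 75% (4 vs 13) and 77% (7 vs 18).

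**Family-wise error of the fixed rule.** The upper bound is m × 0.005: 4.0% for 8 markers, 5.0% for 10, 6.0% for 12.

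**Holm thresholds.** The i-th smallest p-value is compared with 0.05/(m − i + 1), stopping at the first failure. For m = 8 the thresholds run 0.00625, 0.00714, 0.00833, 0.01, 0.0125, 0.0167, 0.025, 0.05. For m = 10 the first is 0.005. For m = 12 it is 0.05/12 = 0.00417.

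**Ordering.** If m is 10 or less, every Holm threshold is at least 0.005. Any p-value at or below 0.005, and every smaller one, therefore passes its threshold, so Holm rejects all that the fixed rule rejects. Simulation found no exception at m = 8 or 10. At m = 12 exceptions occur.

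**Average power per truly changed marker**, by simulation at the stated differences (40,000 trials per setting, eight independent markers):

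| Test | Fixed 0.005 | Holm, 1 changed | Holm, 4 changed | Holm, all 8 changed |
|---|---|---|---|---|
| A paired | 79% | 82% | 86% | 96% |
| B paired | 81% | 83% | 87% | 95% |
| A association (4 vs 13) | 75% | 79% | 83% | 94% |
| B association (7 vs 18) | 77% | 80% | 84% | 94% |

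Correlation between markers trims these gains. At correlation 0.3 the four-marker gain is about 6 to 7 points (B association reaches 83%). At correlation 0.5 with all eight changed, power is 90 to 93%. Simulated Holm family-wise error agrees with the 5% bound within simulation error.

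**Ten markers** (correlation 0.3). With one changed, fixed against Holm is 79.3/79.4 (A paired), 80.8/80.9 (B paired), 75.5/75.6 (A association) and 77.2/77.2 (B association): no gain. With four changed the gain is about 3 points, for example A paired 79.0 to 82.2.

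**Twelve markers** (correlation 0.3). With one changed Holm is worse: A paired 79.2 to 77.0, A association 74.7 to 72.0. With two changed: 79.0 to 77.6 and 75.3 to 73.6. With four the rules are about level.

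**The case against.** The other side has a good case, and most of it stands.

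- **The rule is valid.** For up to 10 markers 0.005 keeps family-wise error within 5%. The plan says why it is there, and the stated detectable differences follow from it. Only an exploratory objective is affected.
- **Eight named against a divisor of 10.** A reader might infer that the plan miscounted or over-corrected. The documents do not support that: the number is approximate and the panel is open to additions, so 10 is a reasonable allowance.
- **The gain depends on the panel and on how many markers move.** With one changed marker among eight, the 2 to 3 points come almost wholly from dividing by 8 instead of 10. With 10 markers and one change there is no gain.
- **Holm is not free for every panel.** A reader might infer that it has no downside. The open panel rules that out, since Holm loses power with 12 markers when few change. The fixed rule's extra power there comes with a family-wise bound of 6%.
- **The family-wise target is inferred.** The plan does not state 5%.

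What remains is that the plan chose to adjust for multiplicity, and for any panel of 10 or fewer a procedure with the same 5% guarantee never rejects less.

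**Conclusion.** The point holds as an efficiency improvement. For 10 or fewer markers the planned rule is valid, and Holm at family-wise 0.05 is never worse. The realistic per-marker gain runs from nothing (10 markers, one true change) through about 3 points (10 markers, four changes) to about 6 to 7 points (eight markers, four changes).

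The figures above 90% might be read as the expected benefit. They need nearly all markers to change by the full detectable difference. Section 18.2 item 4 expects a broad change in the microenvironment on treatment, which lends some support for the paired tests. It does not support, for example, a 2.3 SD association with response in every marker.

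The conclusion rests on two-sided tests, an inferred 5% target, and control applied separately to each family and cohort. Two families in one cohort can together reach 2 × 5% = 10%, as they already can under the plan with 10 markers.

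**What to change.** In Section 18.2 items a and b:

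1. List the markers to be tested and lock the list before analysis. Holm's thresholds depend on the number of markers, which must not be settled after results are seen.
2. Replace the fixed 0.005 with Holm's step-down procedure at a stated family-wise 0.05 (two-sided) over that list. Apply it separately to the baseline-to-Day-28 family and the response-association family in each cohort.
3. Quote detectable differences at the first Holm step, 0.05/m, as conservative planning figures. With 10 markers the present figures stand. With eight, the formula above gives 0.97 SD (A paired), 0.77 (B paired), 2.26 (A association) and 1.69 (B association).

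The cost is wording and an early decision on the panel; there are no new data, tests or patients. The procedure works equally on p-values from the rank-based alternatives the plan allows. If the locked list exceeds 10 markers, expect about 2 to 3 points less power when few markers change (12 markers, one change), in return for keeping the 5% level.
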